8.2.2 Technical Computational Details for Secondary Efficacy Analyses

- 1) Subjects who increase dosages of baseline Crohn’s disease medications or take a new therapy for Crohn’s disease during the trial should be discontinued from the trial, and subjects who withdraw from the trial early are considered as treatment failures in the ITT analysis of the secondary endpoints. These subjects will be considered as non-remission and non-responders for the remission and response endpoints including endoscopic response, PRO-2 remission, clinical response, endoscopic remission.
- 2) For the PRO-2 score used to derive PRO-2 remission, the abdominal pain score is reported as the daily worst abdominal pain (0 to 3) score and the stool frequency score is recorded as the number of loose or watery bowel movements (Bristol stool form scale 6 or 7) per day. The average score of the last 7 day’s data will be used for each component. If a subject has 1 or 2 days’ missing data, the 7 day’s score will be calculated by the average of 6 or 5 days’ data multiplying 7. If more than 2 days’ data are missing, the components’ score will set to be missing.
- 3) No component is allowed to be missing in a PRO related endpoint. PRO-2 remission will be set to missing if either the abdominal pain score or the stool frequency score is missing.

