5.2 Handling of Missing Data

The estimand defining the treatment effect of interest in the protocol uses a mixture of composite strategy and treatment policy strategy specified in the ICH E9 addendum. Subjects who increase dosages of baseline Crohn's disease medications or take a new therapy for Crohn's disease during the trial are considered as treatment failures (non-responders) in the ITT analysis of the primary and secondary endpoints, while these subjects are encouraged to stay in the trial for continuous data collection. These data collected after subjects change their baseline Crohn's disease medication will only be provided in data listings, but not used in the primary and secondary efficacy analyses. In addition, subjects who withdraw from the trial early are considered as treatment failures (non-responders) in the ITT analysis of all of the primary and secondary endpoints. Subjects who discontinue IMP during the trial with no baseline Crohn's disease medication dosage increases and/or new therapy for Crohn's disease through Week 12 are encouraged to stay in the trial and take primary and secondary endpoint evaluations at Week 12 for efficacy analyses. Hence, missing data at Week 12 due to subjects' change of baseline Crohn's disease medication and early withdrawal is handled by an ITT analysis with all these subjects treated as treatment failures (nonresponders).

For CDAI-related endpoints, if a subject has a Week 12 evaluation but a component of the score is missing, the value of the component in the most recent previous visit will be used for the calculation of the score and the endpoint if no more than 2 components of the CDAI score are missing. For a CDAI assessment, if more than 2 components of the score are missing, the CDAI score will be set to missing. This approach is conservative since subjects randomized to OPS-2071 treatment groups are expected to have their Crohn's disease symptoms improved over time. No component is allowed to be missing in a PRO-related endpoint. The abdominal pain and stool frequency scores of PRO-2 are averaged over a 7-day period from the subject's diary.

6 Study Conduct

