- 4) The 3 components of CDAI including liquid or soft stools, abdominal pain and general well-being are collected from the subjects' eDiary. The sum of the scores of the last 7 day's data will be used for each component. If a subject has 1 or 2 days' missing data, the 7 day's score will be calculated by the average of 6 or 5 days' data multiplying 7. If more than 2 days' data are missing, the components' score will set to be missing.
- 5) Clinical remission is defined as CDAI score < 150 for remission subjects as described in session 8.1.1.

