8.2 Secondary Efficacy Endpoints

8.2.1 Secondary Efficacy Analyses

If all both null hypotheses of OPS-2071 600 mg BID, 300 mg BID versus placebo in the primary endpoint of clinical remission are rejected with an experiment-wise Type I error of 0.05 by the test procedure provided in session 8.1.1, a formal test of the secondary efficacy endpoint of endoscopic response (defined as a reduction of the SES-CD by at least 50%) for comparisons of OPS-2071 600 mg BID versus placebo and 300 mg BID versus placebo will be conducted, using a similar procedure used for the primary

endpoint of clinical remission except replacing baseline CDAI with baseline SES-CD score.

The other secondary efficacy endpoints of this trial are listed below by the order of the gatekeeping test procedure:

- 2) Change from baseline in the SES-CD score.
- 3) The percentage of subjects with PRO-2 remission (defined as stool frequency ≤ 3 times per day and abdominal pain ≤ 1) at Week 12.
- 4) The percentage of subjects with clinical response, defined as at least a 25% decrease in the CDAI score, at Week 12.
- 5) The percentage of subjects who, at Week 12, achieve endoscopic remission (defined as a SES-CD score of 0 to 2; or a score of 0 to 4, with no individual subscore greater than 1).
- 6) The percentage of subjects with a decrease from baseline of ≥ 100 points in the CDAI score.

Analysis of secondary endpoint #2 will be conducted using a procedure similar to the analyses of the secondary endpoint of endoscopic response, except the logistic regression will be replaced by an analysis of covariance (ANCOVA). The model used in the analysis of the primary endpoint will be applied to secondary endpoints #3, #4, and #6, while the model used in the analysis of the secondary endpoint of endoscopic response will be applied to the analysis of secondary endpoint #5. The multiplicity handling along with the gatekeeping to protect the experiment wise Type I error in the primary and secondary analyses are detailed in section 8.4.

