A sensitivity analysis of secondary endpoint #3 (PRO-2 remission) of missing data will also be provided similar to the sensitivity analysis of the primary endpoint of CDAI clinical remission. Specifically, missing data for PRO-2 remission will be imputed for the subjects who withdraw from the trial before the Week 12 visit without increasing dosages of baseline Crohn's disease medications or taking a new medication for Crohn's disease during the double-blind treatment period. The missing data under this scenario is considered as MNAR and will be imputed by applying a regression approach¹ to the abdominal pain and stool frequency scores, averaged over a 7-day period. In detail, the placebo-based pattern imputation procedure follows these steps:

- 1) Using Monte Carlo Markov Chain (MCMC) methodology from PROC MI by treatment group to impute the intermittent missing data to a monotone missing pattern;
- 2) Using pattern-mixture model approach to impute the monotone missing data. By applying MNAR statement of PROC MI in SAS, missing values under MNAR will be imputed. Only the observations in the placebo control group will be used

to impute the missing values by using the MODEL option in the MNAR statement. The imputed values for the 3 treatment groups of OPS-2071 will be adjusted using the shift parameter; When the shift parameter is 0, the MI procedure would produce an analysis which is essentially something called “back to placebo”;

- 3) The PRO-2 remission status for the subjects with the imputed data will be determined by checking if the imputed stool frequency score is ≤ 3 and the imputed abdominal pain score is ≤ 1 ;
- 4) Using logistic regression model in the primary analysis to analyze the completed data along with the imputed data;
- 5) Obtaining the overall results using PROC MIANALYZE.

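### SAP 8.2.2 item 2 turns the PRO-2 score into a weekly total when one or two diary days are missing, but still compares it with daily cut-offs

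*SAP*

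**What the plan says.** PRO-2 remission at Week 12 is secondary endpoint #3, defined in SAP 8.2.1 as "stool frequency ≤ 3 times per day and abdominal pain ≤ 1". SAP 8.2.2 item 2 gives the scoring. Stools are counted per day, and "the abdominal pain score is reported as the daily worst abdominal pain (0 to 3) score". With a full diary, "The average score of the last 7 day’s data will be used for each component". With one or two missing days, the "score will be calculated by the average of 6 or 5 days’ data multiplying 7". With more than two missing days the component is set to missing.

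Elsewhere PRO-2 is always on the daily scale. SAP 5.2 says "The abdominal pain and stool frequency scores of PRO-2 are averaged over a 7-day period", and protocol 7.3.1 and 7.4.2 agree. The PRO-2 sensitivity analysis in SAP 8.2.1 imputes "abdominal pain and stool frequency scores, averaged over a 7-day period" and then decides remission by "checking if the imputed stool frequency score is ≤ 3 and the imputed abdominal pain score is ≤ 1".

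The same missing-day wording appears in SAP 8.1.3 item 4 for the CDAI diary components. There the target is a total: "The sum of the scores of the last 7 day's data will be used for each component".

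**The concern.** A mean of the observed days multiplied by 7 estimates a weekly sum. That suits the CDAI, which is built from weekly sums. It does not suit PRO-2, whose cut-offs are per day. No passage gives weekly cut-offs, and the missing-day sentence does not tell the programmer to divide by 7 again. Taken literally, it also allows a pain score of 21 (3 × 7) on an item graded 0 to 3.

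Remission status would then depend on diary completeness as well as symptoms. Two subjects averaging 3 stools and pain 1 per day would be classified differently: the one with seven entries scores 3 and 1 (remission), and the one who missed a day scores 21 and 7 (non-remission).

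At stake are the Week 12 rate in table CT-6.3.1 and its treatment comparison. By-visit PRO-2 remission (SAP 8.3.2, table CT-13.2) refers back to the same definition and would be affected too if it is scored by this rule.

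**Working it through.** The documents give no expected rate or power for PRO-2 remission, so there is no planned figure to reproduce. The limits in step 1 follow from the text alone; steps 2 and 3 rest on assumptions.

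**1. Exact limits.** Let d be the number of recorded days (6 or 5) and S the sum over those days. The daily rule needs S/d ≤ 3 for stools and ≤ 1 for pain. The literal rule needs 7S/d ≤ 3 and ≤ 1.

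| Recorded days | Stool sum, daily rule | Stool sum, literal rule | Pain sum, daily rule | Pain sum, literal rule |
|---|---|---|---|---|
| 6 | 6 × 3 = 18 | 2 (7×2/6 = 2.33; 7×3/6 = 3.5 fails) | 6 × 1 = 6 | 0 (7×1/6 = 1.17 fails) |
| 5 | 5 × 3 = 15 | 2 (7×2/5 = 2.8; 7×3/5 = 4.2 fails) | 5 × 1 = 5 | 0 (7×1/5 = 1.4 fails) |

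A subject averaging 2 stools and pain 0.5 per day meets the daily criteria but scores 14 and 3.5, so is counted as non-remission. Subjects who fail the daily criteria fail the literal rule as well, so the error runs one way only: true remitters are lost.

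**2. Share of affected remitters lost.** Assume Poisson stools, pain of 0 or 1, independent days, and both items missing on the same days. The share lost is 1 − P(stools ≤ 2) × P(no pain) / P(daily criteria met).

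| Assumed symptoms | 5 days | 6 days |
|---|---|---|
| None | 0% | 0% |
| Grade 1 pain on 5% of days, no loose stools | 1 − 0.95^5 = 22.6% | 1 − 0.95^6 = 26.5% |
| 0.5 loose stools per day, no pain | 45.6% | 57.7% |
| 1 loose stool per day, no pain | 87.5% | 93.8% |

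**3. Effect on the comparison (illustration only).** Borrow the CDAI assumption of 40% v 20% from SAP section 4, with 120 (pooled 600 and 300 mg) v 60 subjects. Use a two-sided z-test with pooled null variance in place of the planned logistic model, and ignore the earlier gates. If each diary day is missing independently with probability q, the share of subjects with one or two missing days is P = 7q(1−q)^6 + 21q²(1−q)^5. This gives 0.132, 0.298 and 0.496 for q = 0.02, 0.05 and 0.10. If a fraction f of the affected remissions is lost equally in each arm, the rates become 0.40(1 − fP) and 0.20(1 − fP).

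| Daily completion | f = 0 | f = 0.22 | f = 0.50 | f = 1 |
|---|---|---|---|---|
| 98% | 20.0 points, 78.5% power | 19.4, 77% | 18.7, 74% | 17.4, 69% |
| 95% | 20.0, 78.5% | 18.7, 74% | 17.0, 68% | 14.0, 56% |
| 90% | 20.0, 78.5% | 17.8, 71% | 15.0, 60% | 10.1, 39% |

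The f = 1 column is a bound; the largest share in step 2 is 94%.

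**4. Place in the testing order (SAP 8.4).** Before #3 come three comparisons on the primary endpoint (pooled, 600, 300 mg) and three on endoscopic response, taking its similar procedure to include the pooled test. Then come 150 mg on each of those two endpoints (2) and all four comparisons on #2. The total is 3 + 3 + 2 + 4 = 12.

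**The case against.** The strongest reply is that the intent is plain. The sentence just before specifies an average, as do SAP 5.2, SAP 8.2.1 and the protocol, and a pain score of 21 would look wrong to any programmer. Reading the 7-day score as a sum to be divided by 7 again gives the right answer. That shows what was meant, and the wording does look carried over from the CDAI rule. But 8.2.2 is the computational specification and does not state that step, so two programmers could derive different endpoints from it.

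A second reply is that the direction of bias is not settled, and this stands. If remitters on OPS-2071 have fewer residual symptoms than remitters on placebo, the loss is unequal. With 46% of affected remitters lost on active and 94% on placebo, the step 3 model gives a difference of 20.1 to 20.2 points and power of 81%, 84% and 88% at 98%, 95% and 90% completion. With 22% v 88% lost, the difference is inflated to between 21.2 and 24.4 points. Attenuation follows only if missingness and residual symptoms are equal across arms.

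Three further points stand. The rule works per component, so if only one item has missing days, only that item is rescaled. The power figures rest almost wholly on assumed inputs. And formal testing reaches #3 only after 12 earlier successes, in a trial whose planned analyses will not be performed. These limit the practical consequence; they do not make the rule right.

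**Conclusion.** The concern holds. As written, SAP 8.2.2 item 2 conflicts with its own preceding sentence, with SAP 5.2 and 8.2.1, and with protocol 7.3.1 and 7.4.2. The limits in step 1 are certain, given literal programming and both items missing on the same days. The share of subjects affected is unknown: it depends on diary completion and residual symptoms, which the documents do not give.

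With equal missingness and residual symptoms across arms, the error lowers every arm's remission rate, shrinks the difference and costs power, so it does not favour OPS-2071. With unequal residual symptoms the sign can change. The rate in CT-6.3.1 is affected whether or not #3 is formally tested. The effect on #4 to #6, which #3 gates, arises only if testing gets that far. Subjects with complete diaries or more than two missing days, and the primary CDAI endpoint, are unaffected. This should be fixed as an error in the plan; by SAP section 11 it has no bearing on a reported result.

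**What to change.** In SAP 8.2.2 item 2, delete the multiplication by 7, so that with one or two missing days each PRO-2 component score is the mean of the six or five observed days. The limits then become 18 and 6 over six days, or 15 and 5 over five, on the same scale as a full diary (21 and 7 over seven). Leave the multiplication in SAP 8.1.3 item 4, where the CDAI components are weekly sums. The cost is two words in one sentence, with no new data and no change to any other definition.

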7.4.2 Secondary Endpoint Analysis

If both null hypotheses of OPS-2071 600 mg BID and 300 mg BID versus placebo in the primary endpoint of clinical remission are rejected with an experiment-wise Type I error of 0.05 by the test procedure provided in [Section 7.4.1](#), a formal test of the secondary efficacy endpoint of endoscopic response (defined as a reduction of the SES-CD by at least 50%) for comparisons of OPS-2071 600 mg BID versus placebo and 300 mg BID versus placebo will be conducted, using a similar procedure used for the primary endpoint of clinical remission except replacing baseline CDAI with baseline SES-CD score.

If both null hypotheses of OPS-2071 600 mg BID versus placebo and 300 mg BID versus placebo in the secondary efficacy endpoint are rejected with an experiment wise Type I error of 0.05, the formal comparison of OPS-2071 150 mg BID versus placebo in the primary efficacy endpoint will be conducted, using the same model provided in the previous section for the primary analysis. Again, if the null hypothesis of the primary efficacy endpoint of OPS-2071 150 mg BID is rejected with experiment wise Type I error of 0.05, the formal comparison of OPS-2071 150 mg BID versus placebo in the secondary efficacy endpoint will be conducted, using the same model provided in the previous paragraph for the analysis of the secondary efficacy endpoint. Formal analyses of other secondary efficacy endpoints will start if the null hypothesis of OPS-2071 150 mg BID in the secondary efficacy endpoint of endoscopic response is rejected with experiment wise Type I error of 0.05.

Sensitivity analysis of missing data will be provided in the SAP for this secondary efficacy endpoint.

Protocol 341-201-00004

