8.1.3 Technical Computational Details for Primary Efficacy Analysis

- 1) CDAI score is the sum of 8 components score multiplying by each component's weight factor. The components of CDAI include: number of liquid or soft stools, abdominal pain, general well-being, presence of complications, taking Lomotil or opiates for diarrhea, presence of an abdominal mass, hematocrit, percentage deviation from standard weight. The formula for CDAI score calculation is: sum of number of liquid or soft stools over a week x 2 + sum of abdominal pain over a week x 5 + sum of general well-being over a week x 7 + presence of complications x 20 + taking Lomotil or opiates for diarrhea x 30 + presence of an abdominal mass x 10 + 6 point per percent deviation of hematocrit from 47% in male and 42% in female + percentage below standard weight x 1. One point each is added for each set of complications which include the presence of joint pains (arthralgia) or frank arthritis; inflammation of the iris or uveitis; presence of erythema nodosum, pyoderma gangrenosum, or aphthous ulcers; anal fissures, fistulae or abscesses; other fistulae; fever during the previous week.
- 2) Remission and none remission subjects (ie, treatment failures) are defined as follows:
 - Subjects who complete the trial and meet the primary endpoint definition at Week 12 without increasing dosages of baseline Crohn's disease medications or taking a new medication for Crohn's disease during the double blind treatment period will be considered as remission subjects for the endpoint.
 - Subjects who increase dosages of baseline Crohn's disease medications or take a new medication for Crohn's disease during the double blind treatment period, or subjects who withdraw from the trial during the

double blind period, in addition to the subjects who fail to meet the primary endpoint at Week 12, will be considered as nonremission subjects for the endpoint.

- 3) If a subject has a Week 12 evaluation but a component of the score is missing, the value of the component in the most recent previous visit will be used for the calculation of the score and the endpoint if no more than 2 components of the CDAI score are missing. CDAI score will be set to be missing if more than 2 components' scores are missing.

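### A Week 12 completer without an evaluable PRO-2 is set to missing rather than counted as non-remission, and for SES-CD no rule is stated

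*SAP*

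**What the plan says.** **PRO-2.** SAP 8.2.2 item 2 rescales the diary when 1 or 2 of the 7 days are missing and sets the component to missing beyond that. Item 3 then states: "PRO-2 remission will be set to missing if either the abdominal pain score or the stool frequency score is missing".

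**Failure rule.** SAP 5.2 is limited by cause: "Hence, missing data at Week 12 due to subjects' change of baseline Crohn's disease medication and early withdrawal is handled by an ITT analysis". SAP 8.2.2 item 1 repeats it for the secondary endpoints. It names Crohn's medication change and adds that "subjects who withdraw from the trial early are considered as treatment failures in the ITT analysis of the secondary endpoints".

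**Sensitivity analysis.** For PRO-2, SAP 8.2.1 says that "missing data for PRO-2 remission will be imputed for the subjects who withdraw from the trial before the Week 12 visit", and only if they had no medication change. The primary sensitivity analysis (SAP 8.1.4.1) covers withdrawal and medication change. Protocol 7.4.2 promises a missing-data sensitivity analysis for endoscopic response in the SAP. The SAP text contains none, and its table list (Appendix 4) has one only for CDAI remission and for PRO-2 remission.

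**CDAI.** SAP 8.1.3 item 3 carries forward up to 2 missing components. Beyond that, "CDAI score will be set to be missing if more than 2 components' scores are missing". Item 2 of the same section defines nonremission for the primary endpoint as medication change or withdrawal, "in addition to the subjects who fail to meet the primary endpoint at Week 12".

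**SES-CD.** Neither document says what happens to a completer with no evaluable Week 12 score. Protocol 7.4.2 tests endoscopic response "using a similar procedure used for the primary endpoint of clinical remission except replacing baseline CDAI with baseline SES-CD score".

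**The concern.** The plan presents its secondary response analyses as intent-to-treat with missing outcomes counted as failures, but the rule depends on why the value is missing. Someone who attends Week 12 with too few diary days has neither withdrawn nor changed medication. For PRO-2 the SAP sends that subject to missing, and the sensitivity analysis does not bring the subject back.

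Such subjects are foreseeable. Protocol 3.10 counts those who stop study drug but attend Week 12 as off-treatment completers. The End of Treatment visit omits ileocolonoscopy, and Protocol 3.7.1.9 lists the Week 12 ileocolonoscopy among assessments to be done while the subject is taking study drug. Stopping drug, neglecting a diary or declining a second colonoscopy may each depend on symptoms and may differ by arm. If so, leaving these subjects out biases a comparison that is formally tested in the gatekeeping sequence.

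**Working it through.** **1. Follow a completer with 3 missing diary days and no medication change.**
- PRO-2: 3 exceeds 2, so both components are missing and PRO-2 remission is missing (8.2.2 items 2 and 3). Neither failure reason applies. The imputation does not apply, because the subject did not withdraw.
- CDAI: stools, pain and well-being come from the same diary (8.1.3 item 4). If whole days are blank, all three components are missing. Three exceeds the limit of 2, so carry-forward is not available and CDAI is missing. The primary endpoint may still be caught by the clause on failing to meet it. For endpoints #4 and #6, SAP 8.2.1 carries over the primary model, but it does not say that the nonremission definition comes too.

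**2. Follow a completer without a Week 12 SES-CD.** No rule is found for endpoints #1, #2 or #5. Endpoint #2 uses ANCOVA, so the logistic argument concerns only #1 and #5.

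**3. Check the design inputs** (SAP section 4: 26.5% v 10%, 60 per arm, 2-sided 0.05). Power = Φ[(d − 1.96·s0)/s1], where d is the difference, s0 the standard error under a common rate and s1 under separate rates.
- Individual dose, 60 v 60: (0.165 − 1.96 × 0.0705)/0.0689 = 0.39, power 65.1%. The plan states 65%.
- Pooled, 120 v 60: (0.165 − 1.96 × 0.0644)/0.0559 = 0.69, power 75.6%. The plan states 80%. Of the variants tried, only the arcsine method comes close (79.1%). This does not affect the present point.

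**4. Effect on the estimate.** The missing shares m are assumptions, and every non-evaluable subject is assumed a nonresponder. The apparent rate is then p/(1 − m).
- 10% missing in each arm: 26.5/0.90 − 10/0.90 = 29.4 − 11.1 = 18.3 points, against 16.5.
- 15% active, 5% placebo: 26.5/0.85 − 10/0.95 = 31.2 − 10.5 = 20.7 points.

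**5. Effect on false positives.** The arms are equal under the failure rule. The figure is the chance that a 2-sided 0.05 Pearson test is significant in favour of the drug, by exact enumeration. With 15% v 5% missing, the numbers analysed are 120 × 0.85 = 102 and 60 × 0.95 = 57. The 10% and 20% base rates are the plan's placebo rates for endoscopic response and clinical remission. The 30% rate is an assumption.

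| Base rate | None missing (120 v 60) | 10% in each arm | 15% active v 5% placebo |
|---|---|---|---|
| 10% | 2.2% | 2.2% | 3.4% |
| 20% | 2.3% | 2.2% | 5.1% |
| 30% | 2.4% | 2.5% | 7.0% |

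At the 30% base rate, 10% active v 5% placebo gives 4.0%. The reverse pattern, 5% active v 15% placebo, gives 0.7%.

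**6. Missingness unrelated to outcome.**
- Equal shares of 5% to 20%: the two rules differ by about 0.5 to 2.5 power points (pooled at 20%: 64.9% dropped, 62.4% as nonresponders).
- Unequal shares, 15% v 5%: the nonresponder rule gives 26.5 × 0.85 − 10 × 0.95 = 22.5 − 9.5 = 13.0 points instead of 16.5.

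**The case against.** A reader might infer that SES-CD outcomes are likewise set to missing and deleted. The documents do not support that. The set-to-missing sentence is about PRO-2 only, and testing endoscopic response by a similar procedure could bring in the primary endpoint's residual clause, which would make these subjects nonresponders. That objection stands: for SES-CD the handling is unstated, not wrong. It does not help PRO-2, where item 3 gives an explicit contrary instruction.

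Deletion from the model is also an inference. Neither document says it, although it is the usual treatment of a missing outcome.

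A reader might take 7.0% as the trial's type I error. It is not. It needs three times as much missingness on active as on placebo, every missing subject a nonresponder, and a 30% base rate. It also describes a single stand-alone test. Endoscopic response is tested only after the pooled, 600 mg and 300 mg comparisons succeed on the primary endpoint. PRO-2 comes later still, after endoscopic response, the 150 mg tests and endpoint #2.

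Finally, the nonresponder rule is not free of bias, as step 6 shows. That is a reason to pair it with a sensitivity analysis. It does not justify leaving these completers outside every rule.

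**Conclusion.** The point holds for PRO-2 remission. Followed as written, the SAP makes a formally tested endpoint an observed-case analysis among completers, while section 5.2 declares a nonresponder approach. It holds conditionally for CDAI endpoints #4 and #6, unless the primary endpoint's residual clause is read across. For SES-CD it is a gap with two possible readings.

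The harm is bias under unequal, outcome-related missingness, not lost power. Under the assumptions in the working, the false-positive rate in favour of the drug rises to between 3.4% and 7.0%. With equal shares there is no inflation, and with the pattern reversed the rate falls. The documents give no basis for choosing among these cases.

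No result of this trial is affected: SAP section 11 says the planned analyses will not be performed, because the trial stopped with three randomized subjects. The point matters for the plan and for any reuse of it.

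**What to change.** - In SAP 8.2.2 item 3, replace the instruction to set PRO-2 remission to missing with an instruction to count it as non-remission.
- In SAP 8.1.3 item 2 and 8.2.2 item 1, state that any subject in the analysis set without an evaluable Week 12 value, for whatever reason, is a nonresponder for the primary endpoint and for binary secondary endpoints #1 and #3 to #6.
- Include these completers in the missing-data sensitivity analyses, and add the one that the protocol promises for endoscopic response.
- State separately how a missing Week 12 SES-CD is handled in the ANCOVA for endpoint #2.

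The binary rule costs a few sentences and about one line of programming. The added sensitivity work and the endpoint #2 rule need somewhat more. Reported response rates fall slightly. If missingness is unrelated to outcome but unequal between arms, the nonresponder rule itself shifts the difference, and the sensitivity analyses should show by how much.
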